#### 8 Schedule of Patient Activities

Virtual visits may replace in person clinic visits as relevant. Lab work and disease reassessments must be performed at the enrolling site, unless other arrangements are permitted as discussed with the study PI.

For flexibility "windows" are built into the study calendar to allow for scheduling issues (i.e. holidays, inclement weather, patient request) and may be used as needed. Each time point and its associated window is an independent event and does not affect future time points or the study calendar. This contrasts with treatment delays for toxicity written into the study plan – Refer to Section 6.1.1

Permitted window for scheduling issues:

- A ±1 day window is permitted for visits after Day 1 for Cycles 1 and 2.
- Safety labs may be performed up to 48 hours prior to administration of HCW9218 except for Cycle 2 Day 1 (end of DLT period).
- Beginning with Cycle 3, a ±3 day window is permitted around Day 1 as long as a minimum of 2 weeks separate each HCW9218 in event of a dose delay per Section 6.1.4.
- Imaging studies and tumor markers are performed per standard of care (every 4 cycles (12 weeks) or per SOC if more frequent) windows do not apply.

- End of Treatment (EOT) visit ± 1 week (refer to Section 6.6 for options if the decision to stop treatment is made > 4 weeks after the last dose of HCW9218).
- Follow-up assessments ± 1 month

In addition, a treatment day may be adjusted by the treating Investigator on an individual patient basis if the change is in the best interest of the patient. This may require reporting the change as a study deviation. Contact the study's Regulatory Specialist or Program Manager for guidance. Refer to Section 14.1 for the definition of protocol deviations.

#### 8.1 Standard of Care Activities

Standard of care assessments and procedures are part of good clinical care and are charged to the patient and their health insurance.

	Baseline / screening Within 28 days of Cycle 1 Day 1 unless o/w noted¹	Cycle	1					Cycle	2				Cycle 3 and subsequent cycles	Every 4 cycles (12 weeks) or per SOC if more	End of treatment (EOT) visit 3 weeks after the last dose	After EOT visit: Follow-up for response until PD, then survival only every 3 mon
Study day	-28 to -1 (no Day 0)	1	2	3	5	8	15	1	2	5	8	15	1	frequent until PD	of HCW9218	for 12 months from C1D1
window	Not applicable	±1	day us	sing Day	1 as th	ne anch	or	+3 da	ys for I	Day 1	then ±	£1 day	±3 days	± 14 days	± 1 week	± 1 month
Written consent	X1															
Assess for eligibility	Х															
Medical history including prior cancer treatment	Х															
Concomitant medications	X	Х				Χ	Χ	Χ			Χ	Χ	Х		Х	
AE assessment		Χ	Χ	Х	Χ	Χ	Χ	Χ	Χ	Χ	Χ	Χ	Х		Х	
Physical exam 	Х	Χ				Χ		Χ					Х		Х	
Provider assessment	Х	Х			Χ	Χ	Χ	Χ					Х		Х	
ECOG Performance Status	Х	Χ				Χ		Χ							Х	
Vitals signs	Х	X 3	Χ	Х	Χ	Χ	Χ	X 3	Χ	Χ	Χ	Χ	X 		Х	
Weight  plus height at baseline only	X	X 				Χ		Χ				Χ	Х		X	
CBC with differential	X1	X 	Χ	Χ	Χ	Χ	Χ	Χ	Χ	Χ	Χ	Χ	X 		X	
Complete metabolic panel 	X 	X 				Χ		Χ					X 		Х	
CRP, ferritin, amylase, lipase, LDH, mg, phos	X8					X8										
Diagnosis related biomarker (e.g., CA125, PSA)	Х													Х		Х
Pulmonary function testing only if clinically indicated	Х															
Tumor assessment by disease appropriate methods	X 													Х		Х
Disease response based on RECIST 1.1 (until disease progression)	X 													Х		Х
Survival/follow-up																Х

1. Baseline/Screening – within 14 days of study treatment start for labs required for eligibility; prior disease assessments may be used if they were performed within 42 days of the 1st HCW9218 dose in the absence of intervening anti-cancer therapy. Consent is exempt from 28 day limit and may be performed at any time prior to starting study related activities. If more than 14 days pass between lab work for eligibility (found in Section 4.1.6) and Cycle 1 Day 1, the pre Cycle 1 lab results must continue to meet the criteria in Section 4.1.6.

March 29, 2023 Page 41 of 76 confidential

2. Safety labs can be collected up to 72 hours prior to administration of HCW9218 except for C2 D1 where labs cannot be collected sooner than Cycle 1 Day 22 / Cycle 2 Day 1 (the end of DLT period).

3. C1D1 and C2D1: Vital signs (body temperature, heart rate, respiratory rate, systolic and diastolic blood pressure) are documented before each HCW9218 dose and then after dosing at 15 min (± 5 min), 30 min (± 5 min), 60 min (± 10 min) and 120 min (± 15 min) then hourly (± 15 min) until discharge from the clinic or at completion of dose monitoring.

4. For C3D1 and subsequent doses: Vital signs (body temperature, heart rate, respiratory rate, systolic / diastolic blood pressure) are documented before each HCW9218 dose and then after dosing at 15 min (± 5 min) and 30 min (± 5 min).

#### CPRC #2021LS143 - HCW9218 for Select Advanced Solid Tumors

- 5. HCW9218 dose calculation is based on patient's dose level and actual body weight recorded at Day 1 (or within 14 days prior). Dose adjustments occur only if weight changes by ±10% or greater from weight used to calculate original dose per Section 4.1.
- 6. Cardiac function should be monitored by clinical examination and assessment of vital signs for hypotension, arrhythmia, angina and myocardial infarction. During the study, participants with signs or symptoms of chest pain, murmurs, gallops, irregular rhythm, or palpitations must be further assessed if clinically indicated, including the need for hospitalization
- 7. Complete metabolic panel includes: albumin, alkaline phosphatase, ALT, Anion gap, AST, bilirubin (total), calcium, chloride, CO2, creatinine, glucose, potassium, protein (total), sodium, urea nitrogen
- 8. Baseline and Day 8 measures, repeat only if clinically indicated.

March 29, 2023 Page 42 of 76 confidential

#### 8.2 Research Related Activities

Activities directly related to participation in the research study are paid for by study funding and not charged to the patient or their health plan/health insurance. Research related activities are linked to a standard of care (SOC) visit and may be adjusted to stay with the SOC visit unless otherwise noted.

Tests and procedures	Baseline/ Screening	Cycle 1						Cycle 2					Cycle 3 and all subsequent cycles	Every 4 Cycles (every 12 weeks)	At End of Treatment (EOT visit)
Study day		1	2	3	5	8	15	1	2	5	8	15	Day 1		
Coagulation studies (INR/PTT) 	Х	Χ	Χ	Χ	Χ	Χ	Χ	Χ	Χ	Χ	Χ	Χ			
ECG and cardiac monitoring 	Χ														
Pregnancy testing (serum or urine) for females of child-bearing potential 	Х	X3													
HCW9218 administration (refer to Section 6.1 for dose adjustment based on weight change)		Х						Х					Х		
Targeted toxicity worksheet ( Appendix IV ) in addition to AE assessment per Section 10.2.2		X 	X 	X 	X 										
Blood sample for pharmacokinetics (PK) 		Pre and post 5	X 5	X 5	X 5	X 5		Pre and post 	X 	X 	X 				Х
Blood sample for correlative marker (CM) analysis 		Pre and post 6	X 	Pre and post8	X8	X8	X8	X8							
Blood sample for immunogenicity (IMG) 		X (prior to dose)						X (prior to dose)					X (prior to dose)		Х
Blood sample for immune cell analysis and TIS biomarkers (p16 and p21) (at least 10 mL collected in Heparin tube)		X (prior to dose)				Χ	Х	x (prior to dose)					X (prior to dose)		
Blood sample for UMN research related testing (at least 30 mL collected in 3 Heparin tubes)		X (prior to dose)	X	X	X	Χ	Χ	x (prior to dose)		Х	Χ	Χ	X (prior to dose)		
FACT-G QOL questionnaire (Appendix V)	X													X	Х
Skin condition questionnaire (Appendix VI)								Х					X		Χ
Tumor biopsy (optional refer to Section 4.1.2)	X10												X (prior to cycle 3 dose only)		

- 1- Coagulation studies are performed in FV labs as usual but charge to research, collect prior to day's dose if applicable
- 2- An ECG as usual will be performed at baseline/screening but charged to research.
- 3- A negative serum or urine pregnancy test is required within 14 days prior to enrollment to confirm eligibility for women with childbearing potential (non-childbearing is defined as > 1 year postmenopausal or surgically sterilized). The pregnant test must be repeated (and remain negative) if the baseline testing occurred more than 14 days before Cycle 1 Day 1.

March 29, 2023 Page 43 of 76 confidential

- 4- Targeted toxicity worksheet is completed at the following timepoints per Section 10.2.2: Prior HCW9218 injection on Cycle1 Day 1 (within 1 hour prior to HCW9218), at 3 hours (±15 minutes) and at 6 hours (±15 minutes) post injection, Cycle 1 Day 2, Cycle 1 Day 3, and Cycle 1 Day 5. The completion of the targeted toxicity worksheet aligns with in person visits and may be shifted to align with the actual day a visit occurs or skipped if a visit is not occurred.
- 5- Cycle 1 Blood samples for PK analysis will be collected in association with the first dose of HCW9218: Baseline sample collected within 24 hours prior to HCW9218 dosing, at 30 minutes ± 5 min and 3 hours ± 30 minutes (C1D1), 24 hours ± 6 hours (C1D2), 48 hours ± 6 hours (C1D3), 96 hours ± 24 hours (C1D5) and C1D8 ± 24 hours.
- 6- Cycle 1 Blood samples for CM analysis will be collected in association with the first dose of HCW9218: Baseline sample collected within 24 hours prior to HCW9218 dosing, at 30 minutes ± 5 min and 3 hours ± 30 minutes (C1D1), 24 hours ± 6 hours (C1D2), 48 hours ± 6 hours (C1D3), 96 hours ± 24 hours (C1D5), then on C1D8 ± 24 hours and Day 15 ± 24 hours.
- 7- Cycle 2 Blood samples for PK analysis of HCW9218 will be collected in association with the second dose of HCW9218: Baseline sample collected within 24 hours prior to dose 2 of HCW9218 dosing and at 3 hours ± 30 minutes, 24 hours ± 6 hours (C2D2), 96 hours ± 24 hours (C2D5) and C2D8 ± 24 hours.
- 8- Cycle 2 Blood samples for CM analysis will be collected in association with the second dose of HCW9218: Baseline sample collected within 24 hours prior to dose 2 of HCW9218 dosing and at 3 hours ± 30 minutes, 24 hours ± 6 hours (C2D2), 96 hours ± 24 hours (C2D5) then on C1D8 ± 24 hours and Day 15 ± 24 hours.
- 9- Refer to the HCW Biologics Investigator Initiated Trial (IIT) Manual for sample collection, processing, and shipping details.
- 10- Patients with accessible tumor and who sign the separate consent for a fresh tumor biopsy collected prior to the 1st HCW9218 dose (any time after consent) and before the 3rd dose of HCW9218. Biopsy collection is exempt from the 28 day limit and may be performed at any time after consent and prior to HCW9218 dose. If a biopsy is obtained prior to the 1st HCW9218 dose and a patient is later deemed ineligible to receive treatment, the tumor sample will not be used for research purposes.

March 29, 2023 Page 44 of 76 confidential

Research related sample collection and activities are linked to a standard of care (SOC) visit and may be adjusted to stay with the SOC visit unless otherwise noted.

Up to 3 additional research samples for each test type may be collected at other time points (i.e., at time of AE, disease progression or response) during the study period.

All research samples go to the Masonic Cancer Center Translational Therapy Lab (TTL) except fresh biopsy or surgical samples are handled as described in the contract with BioNet.

Residual samples (and study data) may be used by HCW Biologics Inc. and shared with University of Minnesota investigators for research studies of additional biomarkers and correlative assessments. Results will not influence a patient's treatment nor will the results be provided to the patient or placed in their medical record.

The following testing is performed at HCW Biologics or their designee lab.

**Pharmacokinetic (PK) analysis** – Detection of HCW9218 levels over time. If appropriate, PK may also be performed using the same samples as immunogenicity and correlative marker analysis.

**Immunogenicity (IMG)** - Detection of Anti-HCW9218 Antibodies will be performed at HCW Biologics Inc.

Correlative Marker (CM) Assessments - These tests will be performed at HCW Biologics as research studies using de-identified samples. Serum samples will be collected to evaluate the levels of serum cytokines, chemokines and inflammatory markers, typically but not limited to TGF- $\beta$  isoforms, IL1 $\alpha$ , IL-1 $\beta$ , IL-6, IFN- $\gamma$ , TNF- $\alpha$ , MCP-1, resistin and CRP.

Residual samples (and study data) may be used by HCW Biologics Inc. and shared with University of Minnesota investigators for research studies of additional biomarkers and correlative assessments. Results will not influence a patient's treatment nor will the results be provided to the patient or placed in their medical record.

The following testing is performed at the University of Minnesota.

**Blood Immune Cell Analyses** - Flow and/or mass cytometry analysis of blood cells may be conducted to detect surface markers that define immune cell and lymphocyte subsets (such as NK, NKT, B, and T cells, both CD4 and CD8), as well as intracellular markers that define additional parameters (such as regulatory T

cells (Foxp3) and proliferating cells (Ki67)). RNA sequence analysis may also be conducted to assess the gene expression profile in immune cells.

Quality of Life Assessments Exploratory Research Assessments will be performed on various quality of life parameters. Assessments are completed by the participant or, through oral response to a member of the research team administering the assessment. The Functional Assessment of Cancer Therapy - General (FACT-G) is a validated 27-item questionnaire designed to measure four domains of health related quality of life in cancer patients: physical, social, emotional, and functional well-being using a 5 point Likert-type score based on patient recall of the last 7 days.

**The Skin Condition Questionnaire** is a 3 question binary (Y/N) survey created by HCW Biologics asking about skin changes at the injection site and overall changes in the skin noted by the participant. For yes responses, the participant is asked to describe the changes.

**Tumor Biopsies (Optional)** Patients will be approached based on safety and feasibility of accessible tumor tissue. A separate research biopsy consent is required. Biopsy samples will be stored for future research studies. Immunohistochemistry analysis and genomic, transcriptomic and proteomic molecular profiling may be performed on fresh/frozen and/or formalin-fixed, paraffin embedded (FFPE) tumor tissue. All such analyses will be retrospective and exploratory. Biopsies will be performed according to the institution's standard procedures. Tumors used for biopsy should not be lesions used as RECIST target lesions unless there are no other lesions suitable for biopsy.

# 9 HCW9218 Description, Supply and Potential Toxicities

#### 9.1 Formulation

The inactive ingredients of HCW9218 drug product are the formulation buffer (PBS) comprised of 1.36 g/L of potassium phosphate monobasic ( $KH_2PO_4$ ), 1.43 g/L of sodium phosphate dibasic anhydrous ( $Na_2HPO_4$ ), and 8.18 g/L of sodium chloride (NaCl), pH 7.4.

# 9.2 How Supplied

HCW9218 is an investigational drug product supplied to Investigators by HCW Biologics Inc. at Miramar, Florida. Sufficient HCW9218 drug product will be available for this protocol to treat all of the projected enrolled subjects.

The clinical lot of HCW9218 drug product for use in the study will be provided in 2 mL vials containing 1.0 mL of HCW9218 at a concentration of approximately 20 mg/mL (20 mg HCW9218 in 1 mL phosphate buffered solution). These vials will

be packaged in appropriately sized cartons. HCW9218 drug product vials will be labeled, in accordance with 21 CFR §312.6.

HCW9218 drug product will be packed in a temperature-controlled box and shipped to the study site maintained at a temperature between 2°C to 8°C.

## 9.3 Study Site Storage and Stability

HCW9218 will be received by, stored in, and dispensed by the University of Minnesota, Fairview Investigational Drug Services (IDS) Pharmacy, a secure, limited access facility. Refer to the HCW Biologics Investigator Initiated Trial (IIT) Manual for receipt of the investigational product.

HCW9218 drug product vials will be maintained at a temperature between 2°C and 8°C, protected from excessive light and heat.

Refer to the HCW Biologics Investigator Initiated Trial (IIT) Manual for the reporting of product excursions including storage temperature outside of the recommended temperature range (2°C – 8°C) and/or broken or missing vials.

Note: The Investigator or designee(s) must report excursions by email to HCW by the end of the following business day following the identification and followed by event documentation using the Drug Product Excursion Form (DPEF).

# 9.4 HCW9218 Preparation for Injection

There are no particular hazards associated with HCW9218 and no specific considerations are necessary when handling the vialed product other than handling with gloves.

HCW9218 dose calculation is based on the patient's assigned dose level and actual body weight done on Cycle 1 Day 1 or within the 14 days prior. Dose adjustments occur only if a weight changes by ±10% or greater from the weight used to calculate the Cycle 1 dosing. See Section 6.1.

The calculated amount of HCW9218 will be drawn into a syringe for subcutaneous (SC) injection. The stock concentration is 20 mg/mL, doses will be drawn directly into the syringe for injection.

If the total SC dose is greater than 1.5 mL, the dose will be divided into 2-3 SC injections as needed. Injection sites should be rotated per institutional guidelines and each injection site separated by at least 1 inch.

## 9.5 Investigational Product Accountability and Reordering

IDS, on behalf the study Investigator, will maintain the records of receipt and disposition of the HCW9218 drug product including patient related dates, dose, and quantities administered. IDS tracks the HCW9218 inventory, including expiration dates, and facilitates reordering.

All partially used and unused HCW9218 drug product vials will be destroyed at the IDS per their standard procedures or returned to the HCW according to the established procedures.

Refer to the HCW Biologics Investigator Initiated Trial (IIT) Manual for instructions on reordering the drug product and the return of unused vials at the end of the study.

## 9.6 Possible Interactions with Other Drugs

Potential drug-drug interactions with HCW9218 have not yet been defined.

#### 9.7 Potential Side Effects

HCW9128 has not yet been evaluated in human clinical studies.

Thus, the expected AEs are based on the published clinical experience with other related immunotherapies, including recombinant human IL-2, recombinant human IL-15, TGF $\beta$ RII-Fc fusion and anti-TGF- $\beta$  antibody.

All adverse events listed in Appendix II are defined as "Expected" for the purpose of event documentation and reporting requirements.

Section 7.2 presents the most common and most serious side effects seen in drugs similar to HCW9218 in table format organized by frequency (common, occasional, and rare) as presented in the treatment consent form.

For additional information refer to the Investigator Brochure.

# 10 Event Monitoring, Documentation, and Reporting

Toxicity and adverse events will be classified according to NCI's Common Terminology Criteria for Adverse Events version 5 (CTCAE v5). A copy of the CTCAE can be downloaded from the CTEP home page at

https://ctep.cancer.gov/protocoldevelopment/electronic\_applications/docs/CTCAE\_v5\_Quick\_Reference\_5x7.pdf

The investigational product in this study is the HCW9218.

Event monitoring and documentation begins at the time of the 1st HCW9218 dose and continues through the End of Treatment visit. Active monitoring for adverse events ends

with the End of Treatment visit unless there are ongoing study related toxicity. After the End of Treatment visit through 12 months after the 1st dose of HCW9218, events are documented upon knowledge. Refer to the table in Section 10.2.

### 10.1 Definitions

The following definitions are based on the Code of Federal Regulations Title 21 Part 312.32 (21CFR312.32(a)).

**Adverse Event:** Any untoward medical occurrence associated with the use of a drug in humans, whether or not considered drug related.

**Suspected Adverse Reaction:** Any adverse event for which there is a reasonable possibility that the drug caused the adverse event.

**Life-Threatening Adverse Event or Life-Threatening Suspected Adverse Reaction:** An adverse event or suspected adverse reaction is considered "life-threatening" if, in the view of either the Investigator or Sponsor, its occurrence places the patient or subject at immediate risk of death. It does not include an adverse event or suspected adverse reaction that, had it occurred in a more severe form, might have caused death.

**Serious Adverse Event or Serious Suspected Adverse Reaction:** An adverse event or suspected adverse reaction is considered "serious" if, in the view of either the Investigator or Sponsor, it results in any of the following outcomes:

- Death
- A life-threatening adverse event
- Inpatient hospitalization or prolongation of existing hospitalization
- A persistent or significant incapacity or substantial disruption of the ability to conduct normal life functions
- A congenital anomaly/birth defect
- An important medical event

Unexpected Adverse Event or Unexpected Suspected Adverse Reaction: An adverse event or suspected adverse reaction is considered "unexpected" if it is not listed in the investigator brochure or is not listed at the specificity or severity that has been observed; or, if an investigator brochure is not required or available, is not consistent with the risk information described in the general investigational plan or elsewhere in the current application, as amended.

Note: An IB for HCW9128 is provided by HCW Biologics.

**Expedited (Rapid) Reporting:** Certain events may require rapid notification to entities providing patient safety oversight (e.g. IRB). Refer to Section 10.3.

## 10.2 Event Monitoring and Documentation

Event monitoring and documentation begins at the time of the 1st HCW9218 dose and continues through the End of Treatment visit. Active monitoring for adverse events ends with the End of Treatment visit unless there are ongoing study related toxicity. After the EOT through 12 months from Cycle 1 Day 1 (follow-up for response and survival), events are documented upon knowledge. Refer to the table below:

Event	Active Treatment Period		During follow-up for
	Cycle 1 Day 1 through	Cycle 2 Day 1 through	12 months from
	the end of DLT	though End of	Cycle 1 Day 1
	observation period and	Treatment (EOT) visit	(events are
	the DLT assessment is		documented upon
	completed		knowledge)
Any event meeting the definition of serious	X	X	X 1
regardless of attribution or expectedness	^	Λ	^
Any death (date and cause)	Χ	Χ	Χ
1st incidence of a pre-defined adverse event	X 		
during Fast-track enrollment per Section 6.2.1	Λ-		
Any event meeting the definition of a Dose	X3		
Limiting Toxicity (DLT)	Λ'		
All ≥Grade 2 AEs regardless of attribution (see	X	X	
exceptions in Section 10.2.1)	^	^	
Targeted Toxicity Worksheet (Appendix IV) –	X (refer to schedule in		
record all AE grades	Section 10.2.2)		

- 1. Events are documented upon knowledge if they are unexpected and at least possible related to HCW9218.
- 2. Used only once to trigger change from 1 patient cohort to 3 patient cohort and move to Stage 1 Step 2 or Stage 2 (if a DLT also occurs).
- 3. Stage 1: Any event meeting the definition of DLT is in association with the 1st treatment cycle (through the end of the DLT period) is also be reported as a DLT event contributing to subsequent dose cohort decisions per Section 12. Stage 2 (CRM component) event Section 13.4.

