# 6.6 Duration of Study Treatment

A minimum of two treatment cycles is planned and HCW9218 may continue until disease progression unless any one of the following occurs sooner:

- Patient requests to discontinue treatment early if in agreement, follow-up would continue as in Section 6.7 unless the patient also withdraws consent.
- In the judgement of the treating Investigator and documented in the medical record, study treatment is no longer in the best interest of the participant.

An End of Treatment (EOT) visit occurs 3 weeks (±1 week) after the last dose of HCW9218 to confirm no ongoing side effects/toxicity. If ongoing toxicity at the EOT visit, it should be managed as medically appropriate and documented, it if meets the criteria for documenting as an AE be followed until resolution or stabilization.

In the situation where a patient's EOT visit falls outside of the visit window due to a prolonged period before the decision to discontinue treatment is made, the EOT related activities may be retrospectively abstracted from the medical record from around the time the EOT would have occurred and/or delayed until the next standard of care visit. Missing items / research samples will not be considered a deviation.

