containing the TGF $\beta$ RII domain were also well-tolerated at i.v. dose levels up to 15 mg/kg with reported treatment-emergent skin lesions and mucosal bleeding being associated with TGF- $\beta$  inhibition. The combination of IL-15 immunostimulatory and TGF- $\beta$  antagonist activities in HCW9218 may result in additional and/or more frequent or severe AEs.

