# 10.3 Required Reporting: IRB, HCW Biologics and FDA

Certain events or situations require rapid (expedited) reporting as summarized in the table below as well as reporting to the FDA as a part of the IND annual report.

Agency reporting to	Criteria for reporting	Timeframe	Form to Use	Submit to
U of MN IRB	Unanticipated death of a locally enrolled subject(s); New or increased risk; Any adverse event that requires a change to the protocol or consent form – refer to the IRB website for complete details	5 Business Days	RNI	ETHOS
	Deviations that occur at UMN as defined in Section 14.1	Per current IRB requirements	OnCore Deviation Form and IRB Report Form	
FDA	Unexpected and fatal or unexpected and life threatening suspected adverse reaction  1) Serious, unexpected, and suspected adverse reaction or 2) Increased occurrence of serious suspected adverse reactions over that listed in the investigator brochure or 3) Findings from other sources (other studies, animal or in vitro testing) – not applicable for this study	No later than 7 Calendar Days  No later than 15 Calendar Days	University of Minnesota SAE Report	Submit to FDA as an amendment to IND with a copy to HCW Safety Reporting <[contact]></[contact]>
	All other events per CFR 312.32	At time of annual report	FDA Annual report	Submit to FDA as an amendment to IND
HCW Biologics	Any event meeting the definition of an SAE	Within 24 hours of study team knowledge	University of Minnesota SAE Report	Submit to: HCW Safety Reporting <[contact]></[contact]>

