disorders	Chronic kidney disease	Х		
Respiratory, thoracic	Adult respiratory distress syndrome	Х		
and mediastinal	Allergic rhinitis	Х	Х	
disorders	Apnea	Х		
	Cough	Х		
	Dyspnea	Х	Х	
	Epistaxis			X
	Laryngeal hemorrhage	Х		Х
	Pleural effusion		Х	
	Pneumothorax	Х		
	Pulmonary edema	Х		
	Respiratory failure	Х		
	Pharyngeal mucositis	Х		
	Tracheal fistula	Х		
Skin and subcutaneous	Dry skin		Х	
tissue disorders	Erythroderma	Х		
	Hyperkeratosis			X
	Pruritus	Х	Х	Χ
	Other, actinic keratosis			X
	Other, basal cell carcinoma			X
	Other, keratoacanthoma			Х
	Other, lichenoid keratosis			X
	Other, squamous cell carcinoma			Х
	Rash acneiform	Х		
	Rash maculo-papular	Х	Х	Х
	Stevens-Johnson syndrome	Х		
	Urticaria	Х		
Vascular Disorders	Arterial thromboembolism	Х		
	Capillary leak syndrome	Х		
	Hypertension		Х	
	Hypotension	Х	Х	
	Other, mucosal bleeding		Х	X
	Phlebitis	Х		
	Thromboembolic event	Х		
	Vasculitis	Х		

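### Footnote 1 in Section 10.2 lets non-fatal, related but expected serious events that start after the End of Treatment visit be left out of the study's safety record, in conflict with Section 10.3

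*Combined protocol and SAP*

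**What the plan says.** The Section 10.2 table has a row for serious events, which it labels as applying "regardless of attribution or expectedness". In the two active-treatment columns the row is unrestricted. In the follow-up column the entry carries footnote 1: "Events are documented upon knowledge if they are unexpected and at least possible related to HCW9218".

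Three other provisions determine what that footnote does:

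- **What counts as expected.** Sections 7.2 and 9.7 define all Appendix II terms as expected for both documentation and reporting. The list includes myocarditis, colitis, capillary leak syndrome, intracranial hemorrhage, keratoacanthoma and "Other, squamous cell carcinoma". Section 10.1 instead defines an unexpected event against the investigator brochure, taking specificity and severity into account.
- **When the footnote starts and stops.** Section 10.2 states: "Active monitoring for adverse events ends with the End of Treatment visit unless there are ongoing study related toxicity". Section 6.6 sets the visit: "An End of Treatment (EOT) visit occurs 3 weeks (±1 week) after the last dose of HCW9218". Documentation upon knowledge then runs to 12 months from Cycle 1 Day 1.
- **What must be reported.** The HCW Biologics row of Section 10.3 covers "Any event meeting the definition of an SAE", within 24 hours of the team learning of it. It has no condition on expectedness, relatedness or time.

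**The concern.** HCW9218 had no human data when this text was written, and its expected list is borrowed from other agents. Section 7.1 warns that combining the two mechanisms may make adverse events more frequent or more severe. Whether listed events are more frequent can be judged only if listed events are counted. After EOT, footnote 1 stops requiring that count for the events the plan itself anticipates.

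Two uses of the data are affected. The secondary objective is the safety of repeat dosing, measured by adverse event incidence, and Section 13.2 estimates it as a proportion. Section 10.3 also has a 15-day FDA criterion based on an increase in serious suspected reactions over the brochure, which depends on counts of expected reactions. In addition, the 12-month limit runs from the first dose while treatment may continue until progression, so patients with the longest exposure have the least time after treatment under documentation.

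**Working it through.** **1. Which events fall through.** Take a serious event that is non-fatal, at least possibly related, on the Appendix II list, and first appears after EOT.

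| Provision | Is this event captured? |
|---|---|
| 10.2 row label | Yes, attribution and expectedness are irrelevant |
| 10.2 text above the table | Yes, upon knowledge, with no expectedness filter |
| 10.2 footnote 1 with 7.2 and 9.7 | No, because it is expected |
| 10.2 footnote 1 with 10.1 | Only if it exceeds the brochure's listed specificity or severity |
| 10.3, HCW Biologics row | Yes, as an SAE report within 24 hours of knowledge |

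The provisions give different answers for the same event. Staff following Section 10.3 would send the supplier an event that footnote 1 does not require in the study record. Appendix II adds to the uncertainty: it lists terms without severity, and its own introduction ties the expected label to expedited reporting only, whereas Sections 7.2 and 9.7 extend it to documentation.

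**2. When the filter begins.** Section 6.6 gives 3 weeks ± 1 week: 21 − 7 = 14 days and 21 + 7 = 28 days after the last dose. The upper edge agrees with Section 8, which refers to Section 6.6 when the decision to stop comes more than 4 weeks after the last dose.

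**3. How long the filter applies.** Count the first dose as day 0, with 21-day cycles and no delays. The last of *k* doses falls on day 21(*k* − 1), so

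days left to month 12 = 365 − [21(*k* − 1) + 14 to 28].

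| Doses | EOT (day) | Days left to 365 |
|---|---|---|
| 1 | 14 to 28 | 337 to 351 |
| 2 | 35 to 49 | 316 to 330 |
| 8 | 161 to 175 | 190 to 204 |
| 17 | 350 to 364 | 1 to 15 |
| 18 | 371 to 385 | none |

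After the planned minimum of two doses, 316/365 = 87% to 330/365 = 90% of the year falls under footnote 1. From 18 doses, EOT comes after the 12-month limit and observation after the last dose ends with EOT, at 14 to 28 days. Delayed or skipped doses would bring this about at a lower dose count.

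**The case against.** The strongest reply is that little is really lost. Deaths are recorded with date and cause in every period. Toxicity ongoing at EOT is followed to resolution or stabilization under Section 6.6. A known late SAE still produces a report to HCW Biologics. A listed event worse than the brochure describes is unexpected under Section 10.1. A footnote that narrows one column is also ordinary table drafting. All of this stands, and it confines the gap to non-fatal, related, expected serious events with onset after EOT. It does not close the gap: a supplier report is not an entry in the study's own event record, and Section 10.3 has no matching restriction.

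A reader might infer that late cases of the named risks go wholly unrecorded, or that the increased-occurrence criterion cannot be applied. The documents do not support either. Section 10.3 still captures SAEs the team learns of, and all on-treatment serious events are documented whatever their expectedness.

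A reader might also infer that these risks are known to appear late. Section 7.1 speaks only of agents "with reported treatment-emergent skin lesions and mucosal bleeding being associated with" TGF-β inhibition, which says nothing about late onset. Section 7.2 puts skin lesions at 3 or fewer per 100 people on similar drugs, so at most 24 × 0.03 = 0.72 cases in 24 patients, at any time and of any seriousness.

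Finally, day 14 is only the earliest edge of a visit planned for day 21, and Section 6.6 allows it to be later. The window itself is not an error.

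**Conclusion.** The point holds as a conflict in the event-collection rules with a limited but real consequence. Followed as written, footnote 1 with Sections 7.2 and 9.7 permits related, expected, non-fatal serious events with onset after EOT to be omitted from the study's safety record. That can undercount related SAEs for the repeat-dosing objective and weakens, without disabling, the increased-occurrence criterion. DLT assessment and the MTD are untouched, because DLTs are confined to the first cycle.

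The 87% to 90% figure is calendar time under the filter, not a share of events lost. The number of events at stake cannot be estimated, because the documents give no late-onset rate. The absence of any post-EOT documentation period from about 18 doses assumes undelayed 21-day cycles, and the documents do not indicate how many patients would reach that point.

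**What to change.** - Replace footnote 1 with: *serious events at least possibly related to HCW9218 are documented upon knowledge, whether expected or unexpected.*
- State that the remaining relatedness limit is a deliberate narrowing of the row label for the follow-up column, and reconcile it with Section 10.3, which has no such limit.
- Reconcile the two definitions of expectedness (the brochure-based one in Section 10.1 and the Appendix II list), including whether the list governs documentation or only expedited reporting.
- State that upon-knowledge documentation of related serious events also applies after EOT for patients whose EOT falls near or after 12 months from Cycle 1 Day 1.

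The cost is protocol wording and a few more SAE forms. No visits or procedures are added: within the 12-month period, Section 6.7 already allows follow-up by record review or through the local physician.
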